8.4 Informed consent

The Investigator will:

- Ensure each subject is given full and adequate oral and written information about the nature, purpose, possible risk, and benefit of the study
- Ensure each subject is notified that they are free to discontinue from the study at any time
- Ensure that each subject is given the opportunity to ask questions and allowed time to consider the information provided

- Ensure each subject provides signed and dated informed consent before conducting any procedure specifically for the study
- Ensure the original, signed Informed Consent Form(s) is/are stored in the Investigator's Study File
- Ensure a copy of the signed Informed Consent Form is given to the subject
- Ensure that any incentives for subjects who participate in the study as well as any provisions for subjects harmed as a consequence of study participation are described in the Informed Consent Form that is approved by the IRB

8.5 Changes to the protocol and informed consent form

Study procedures will not be changed without the mutual agreement of the Investigator and AstraZeneca.

If there are any substantial changes to the CSP, then these changes will be documented in an Amendment and where required in a Revised CSP.

The Amendment is to be approved by the relevant IRB and if applicable, also the national regulatory authority, before implementation. Local requirements are to be followed for Revised CSPs.

AstraZeneca will distribute any subsequent Amendments and new versions of the CSP to the Investigator. For distribution to the IRB see Section 8.3.

If an Amendment requires a change to the Informed Consent Form, AstraZeneca, and the IRB are to approve the revised Informed Consent Form before the revised form is used.

If local regulations require, any administrative change will be communicated to or approved by the IRB.

8.6 Audits and inspections

Authorized representatives of AstraZeneca, a regulatory authority, or the IRB may perform audits or inspections at the study center, including source data verification. The purpose of an audit or inspection is to systematically and independently examine all study-related activities and documents, to determine whether these activities were conducted, and data were recorded, analyzed, and accurately reported according to the CSP, ICH/GCP guidelines, and any applicable regulatory requirements. The Investigator will contact AstraZeneca immediately if contacted by a regulatory agency about an inspection at the study center.

9. STUDY MANAGEMENT BY

Study management will be performed by _____ on behalf of AstraZeneca.

9.1 Pre-study activities

Before the first subject is entered into the study, it is necessary for _____ to:

- Determine the adequacy of the facilities
- Determine availability of appropriate subjects for the study
- Discuss with the Investigator (and other study center personnel involved with the study) their responsibilities with regard to CSP adherence, and the responsibilities of _____ and AstraZeneca. This will be documented in a Clinical Study Agreement

9.2 Training of study center personnel

Before the first subject is entered into the study, _____ will review and discuss the requirements of the CSP and related documents with the study center personnel and also train them in any study-specific procedures and system(s) utilized.

The Investigator will ensure that appropriate training relevant to the study is given to all of these personnel, and that any new information relevant to the performance of this study is forwarded to the personnel involved.

The Investigator will maintain a record of all individuals involved in the study (medical, nursing, and other personnel).

9.3 Monitoring of the study

During the study, a _____ monitor will have regular contact with the study center, including visits to:

- Provide information and support to the Investigator
- Confirm that facilities remain acceptable
- Confirm that the study center personnel are adhering to the CSP, that data are being accurately and timely recorded in the eCRFs, that biological samples are handled in accordance with the Laboratory Manual, and that investigational product accountability checks are being performed
- Perform source data verification (a comparison of the data in the eCRFs with the subject's medical records at the hospital or practice, and other records relevant to the study) including verification of informed consent of participating subjects. This will require direct access to all original records for each subject (eg, clinic charts)

- Ensure withdrawal of informed consent to the use of the subject's biological samples is reported and biological samples are identified and disposed of or destroyed accordingly, and the action is documented and reported to the subject

The monitor will be available between visits if the Investigator or other study center personnel needs information and advice about the study conduct.

9.3.1 Source data

Refer to the Clinical Study Agreement for the location of the source data.

9.4 Study agreements

The Investigator at the study center should comply with all the terms, conditions, and obligations of the Clinical Study Agreement, or equivalent, for this study. In the event of any inconsistency between this CSP and the Clinical Study Agreement, the terms of the CSP shall prevail with respect to the conduct of the study and the treatment of subjects. In all other respects not relating to study conduct or treatment of subjects the terms of the Clinical Study Agreement shall prevail.

Agreements between AstraZeneca, and the Investigator should be in place before any study-related procedures can take place, or subjects are enrolled.

9.4.1 Archiving of study documents

The Investigator follows the principles outlined in the Clinical Study Agreement.

9.5 Study timetable and end of study

The end of the study is defined as 'the last visit of the last subject undergoing the study'.

The clinical conduct of this study is expected to start in and to end by

The study may be terminated at the study center if the study procedures are not being performed according to GCP, or if recruitment is slow. AstraZeneca may also terminate the entire study prematurely if concerns for safety arise within this study or in any other study with ticagrelor.

10. DATA MANAGEMENT BY

Data management will be performed by

The data collected through third party sources will be obtained and reconciled against study data.

Adverse events and medical/surgical history will be classified according to the terminology of the latest version the Medical Dictionary for Regulatory Activities (MedDRA). Medications

will be classified according to the AstraZeneca Drug Dictionary. All coding will be performed by Data Management.

Data queries will be raised for inconsistent, impossible, or missing data. All entries to the study database will be available in an audit trail.

The data will be validated as defined in the Data Management Plan. Quality control procedures will be applied to each stage of data handling to ensure that all data are reliable and have been processed correctly.

When all data have been coded, validated, and locked, clean file will be declared. Any treatment revealing data may thereafter be added and the final database will be locked.

Data associated with biological samples will be transferred to laboratories internal or external to AstraZeneca.

11. EVALUATION AND CALCULATION OF VARIABLES BY

11.1 Calculation or derivation of safety variable(s)

Where appropriate, change from baseline variables will be calculated for continuous variables as the post-treatment value minus the value at baseline. Baseline for the statistical analyses will be defined as:

- Clinical laboratory tests: Day -1
- Vital signs: Day 1 pre-dose

If a subject is missing the baseline collection, the previous non-missing evaluation in the period will become the baseline value. If no baseline or previous to baseline evaluations exist, then the baseline value will be treated as missing.

11.1.1 Other significant adverse events

During the evaluation of the AE data, an AstraZeneca medically qualified expert will review the list of AEs that were not reported as SAEs and discontinuation due to AEs. Based on the expert's judgment, significant AEs of particular clinical importance may, after consultation with the Global Patient Safety Physician, be considered other significant adverse events (OAEs) and reported as such in the CSR. A similar review of other safety data will be performed for identification of OAEs.

Examples of these are marked hematological and other laboratory abnormalities, and certain events that lead to intervention (other than those already classified as serious), dose reduction, or significant additional treatment.

11.2 Calculation or derivation of pharmacokinetic variables

The PK analysis of ticagrelor and its metabolite AR-C124910XX will be the responsibility of the Pharmacokineticist at . Standard Operating Procedures and Work Instructions will be used as the default methodology if not otherwise specified. Actual sampling times will be used for the computation of PK parameters.

Pharmacokinetic parameters will be derived using standard non-compartmental methods with WinNonlin[®] Professional Version 5.2, or higher

All PK computations will be performed using WinNonlin[®] Professional Version 5.2 (or higher) or SAS[®] Version 9.2 or higher

Graphics will be prepared using SAS[®] Version 9.2 and Sigmaplot[®] 9.0

Subjects who withdraw from the study following dosing, but prior to study completion, will be included in the PK analysis provided they have evaluable concentrations over the planned collection period. Subjects with partial data will be evaluated on a case-by-case basis to determine if sufficient data are available for meaningful analysis.

If data permits, the following plasma PK parameters will be calculated for ticagrelor and its metabolite AR-C124910XX:

- Observed maximum plasma concentration (C_{\max})
- Time to maximum concentration (t_{\max})
- Area under plasma concentration-time curve from zero to the last measurable concentration [$AUC_{(0-t)}$]
- Area under plasma concentration-time curve from zero to infinity (AUC)
- Terminal half-life ($t_{1/2}$)

Additionally, the following will be computed for Treatments A and C:

- AR-C124910XX: ticagrelor ratios for C_{\max} , $AUC_{(0-t)}$, and AUC

Similarly, if data permits the following pharmacokinetic parameters will be calculated for cyclosporine in whole blood:

- Observed maximum whole blood concentration (C_{\max})
- Time to maximum concentration (t_{\max})
- Area under whole blood concentration-time curve from zero to the last measurable concentration [$AUC_{(0-t)}$]

- Area under whole blood concentration-time curve from zero to infinity (AUC)
- Terminal half-life ($t_{1/2}$)

The following PK diagnostic parameters will be calculated for all analytes, as appropriate, and will be listed, but not summarized:

- The time interval ($t_{1/2}$, interval) of the log-linear regression to determine $t_{1/2}$
- Number of data points ($t_{1/2}$, N) included in the log-linear regression analysis to determine $t_{1/2}$ (a minimum of 3 points will be used)
- Regression coefficient (Rsqr), a goodness-of-fit statistic for calculation of λ_z . If Rsqr is less than 0.80, then $t_{1/2}$ and related parameters will not be reported
- Percent AUC that is extrapolated (%AUCext)

If %AUCext is greater than 20% then AUC will not be reported.

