13.1	Medical emergencies and AstraZeneca contacts	45
13.2	Overdose	45
13.3	Pregnancy.....	46
13.3.1	Maternal exposure.....	46
13.3.2	Paternal exposure.....	46
14.	LIST OF REFERENCES	47

LIST OF TABLES

Table 1	Study assessments	14
Table 2	Identity of investigational products	22
Table 3	Safety laboratory variables	30
Table 4	Volume of blood to be drawn from each subject.....	32

LIST OF FIGURES

Figure 1	Study design flow chart	14
----------	-------------------------------	----

LIST OF APPENDICES

Appendix A	Signatures (Not Applicable)
Appendix B	Additional Safety Information
Appendix C	International Airline Transportation Association (IATA) 6.2 Guidance Document
Appendix D	Optional Biomarker Research Samples

LIST OF ABBREVIATIONS AND DEFINITION OF TERMS

The following abbreviations and special terms are used in this study Clinical Study Protocol.

Abbreviation or special term	Explanation
%AUC _{ext}	Percent of area extrapolated for area under the plasma concentration-time curve from zero to infinity
λ_z	Terminal rate constant
ACS	Acute coronary syndromes
ADP	Adenosine diphosphate
AE	Adverse event (see definition in Section 6.3.1)
ALP	Alkaline phosphatase
ALT	Alanine aminotransferase
ASA	Acetylsalicylic acid
AST	Aspartate aminotransferase
AUC	Area under the plasma concentration-time curve from zero to infinity
AUC _(0-t)	Area under the plasma concentration-time curve from zero to the last measurable concentration
B	Blood
BLQ	Below the lower limit of quantification
BMI	Body mass index
CI	Confidence interval
C _{max}	Maximum plasma concentration
CPA	Clinical Pharmacology Alliance
CSP	Clinical Study Protocol
CSR	Clinical Study Report
CV	Coefficient of variation
CYP	Cytochrome P450
DAE	Discontinuation due to adverse event
DBP	Diastolic blood pressure
ECG	Electrocardiogram
eCRF	Electronic Case Report Form
FDA	Food and Drug Administration
GCP	Good Clinical Practice

Abbreviation or special term	Explanation
GGT	Gamma-glutamyl transferase
GMP	Good Manufacturing Practice
H	High
HBsAg	Hepatitis B surface antigen
HCV	Hepatitis C virus
HIV	Human immunodeficiency virus
IATA	International Air Transport Association
ICH	International Conference on Harmonization
IRB	Institutional Review Board
L	Low
LLOQ	Lower limit of quantification
MTD	Maximum tolerated dose
MedDRA	Medical Dictionary for Regulatory Activities
NA	Not Applicable
ND	Not Determined
NSTEMI	Non-ST segment elevation myocardial infarction
OAE	Other significant adverse event (see definition in Section 11.1.1)

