Physical examination	√	√ ^c			√ ^c	√

Table 1 Study assessments

Assessment	Visit 1	Visits 2, 3, and 4				Visit 5
	Screening	Treatment visits 1, 2, and 3				Follow-up
	Days -28 to -2	Day -1	Day 1	Day 2	Day 3	7 to 10 days
Vital signs	√	√	√	√	√	√
12-Lead paper ECG	√	√			√	√
Admission		√				
Randomization			√ ^b			
Investigational product administration			√			
Clinical chemistry and hematology	√	√			√	√
Urinalysis	√	√			√	√
Screen for hepatitis and HIV	√					
Screen for drugs of abuse	√	√				
Alcohol breath test	√	√				
Pharmacokinetic sampling ^d			√	√	√	
Concomitant medications	√	√	√	√	√	√
Adverse events		√	√	√	√	√
Serious adverse events	√	√	√	√	√	√
Discharge					√	

a At Visit 1 (screening) or on Day -1 of Visit 2.

b Visit 2 only.

c Only targeted physical examination: general, cardiovascular system, chest, abdomen, and skin.

d Venous blood will be collected pre-dose and at 0.5, 1, 2, 3, 4, 6, 8, 12, 18, 24, 36, and 48 hours post-dose for the determination of cyclosporine, ticagrelor and AR-C124910XX.

ECG: Electrocardiogram; HIV: Human immunodeficiency virus.

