3.2 Rationale for study design, doses and control groups

This study design is in line with the Food and Drug Administration (FDA) guidance for Industry for drug-drug interaction studies ([FDA Guidance for Industry, Drug Interaction Studies 2006](#)). An open-label design is acceptable as no pharmacodynamic (PD) endpoints are critical to the assessment of the interaction.

The rationale for choosing healthy subjects is to investigate the potential interaction of ticagrelor and cyclosporine without adding additional confounding factors, such as disease state or concomitant medications. The study is restricted to male subjects as there is a possibility for a gender effect during the female menstrual cycle when drugs are metabolized by CYP3A. By including men only, the possible variability factor is removed.

Ticagrelor will be administered as a single 180 mg dose. Ticagrelor (180 mg loading dose; 90 mg twice daily thereafter) is approved in the European Union and in the United States of America (USA) for the prevention of thrombotic events in patients with ACS. The 180 mg single dose was selected for this study as it is the recommended loading dose and also the highest approval dose expected to be administered to patients. The PK of ticagrelor appeared linear and the maximum plasma concentration (C_{max}) and the area under the plasma concentration-time curve from zero to infinity (AUC) of ticagrelor and AR-C124910XX increased approximately in a dose-proportional manner over the dose range of 30 to 1260 mg. Since no time-dependent changes in ticagrelor PK over the course of multiple dosing were observed during its clinical development and mean accumulation ratios at 90 mg twice daily dosing was approximately 1.8 for ticagrelor and AR-C124910XX, a 180 mg single dose would provide the exposure to ticagrelor and AR-C124910XX higher than those following multiple 90 mg twice daily dosing. Thus, a single dose of 180 mg dosing not only results in a simple study design, but also maximizes the potential impact of ticagrelor on the interaction drug (cyclosporine).

Cyclosporine will be administered as a single 600 mg dose. Plasma concentrations of cyclosporine as a P-gp inhibitor range from 1000 to 5000 ng/mL and a single 300 mg dose of cyclosporine produces a mean plasma concentration of approximately 1000 ng/mL. Therefore, a single 600 mg cyclosporine dose will be administered in this study to provide sufficient exposure to investigate the potential effect on P-gp.

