12.2 Methods of statistical analyses

12.2.1 General principles

The statistical analyses will be performed using SAS[®], Version 9.2 or higher. Standard Operating Procedures and Work Instructions will be used as the default methodology if not otherwise specified.

Missing data will result in a reduced sample size for that parameter. No action will be taken to handle missing data.

No adjustment for multiplicity will be made.

A subject who withdraws prior to the last planned observation in a study period will be included in the analyses up to the time of discontinuation.

All data will be included in the data listings. Any data excluded from the summaries and statistical analyses will be flagged accordingly.

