The PK parameters for ticagrelor, AR-C124910XX, and cyclosporine will be natural log-transformed prior to analysis. The natural log-transformed AUC and C_{\max} data will be separately analyzed using a mixed effects model with terms for treatment, period, and sequence as fixed effects and subject nested within sequence as a random effect. The estimated least squares means and intra-subject variability from the mixed effects model will be used to construct 90% confidence intervals (CIs) for the difference in means on the log scale between the 2 treatments. The treatment effect and its corresponding 90% CIs will be back-transformed using anti-logarithms to its original scale and reported as ratio of treatments (ticagrelor + cyclosporine / ticagrelor alone or ticagrelor + cyclosporine / cyclosporine alone).

- If the 90% CIs for both AUC and C_{\max} for the effect of cyclosporine on ticagrelor are entirely contained within the pre-specified range of 0.80 to 1.25 then it will be conclude that a single 600 mg dose of cyclosporine has no effect on the PK of ticagrelor
- Also, if the 90% CIs for both AUC and C_{\max} for the effect of ticagrelor on cyclosporine are entirely contained within the pre-specified range of 0.80 to 1.25, then it will be conclude that a single 180 mg dose of ticagrelor has no effect on the PK of cyclosporine

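### Withholding AUC above 20% extrapolation can pull the primary AUC ratio towards 1 if the interaction prolongs half-life, and the protocol fixes no analysis that would show it

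*Protocol*

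**What the plan says.** Protocol Section 11.2 sets the reliability rule: "If %AUCext is greater than 20% then AUC will not be reported". AUC here is the "area under the plasma concentration-time curve from zero to infinity". Section 12.2.1 adds: "Missing data will result in a reduced sample size for that parameter. No action will be taken to handle missing data".

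In Section 12.2.4 the log-transformed AUC and Cmax "data will be separately analyzed using a mixed effects model" with treatment, period and sequence as fixed effects and subject within sequence as random. Each no-effect conclusion requires the 90% intervals for both AUC and Cmax to lie within 0.80 to 1.25. AUC(0-t) is derived in Section 11.2 but is not named among the modelled parameters. The extrapolated percentage is listed for each profile and not summarised.

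Sampling is the same in every period (Table 1, note d): "Venous blood will be collected pre-dose and at 0.5, 1, 2, 3, 4, 6, 8, 12, 18, 24, 36, and 48 hours post-dose". No half-life is given for any analyte. The nearest figure is in Section 3.2: "mean accumulation ratios at 90 mg twice daily dosing was approximately 1.8 for ticagrelor and AR-C124910XX".

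**The concern.** Sampling stops at 48 h, so the extrapolated share depends on half-life. Sections 1.1 and 1.2 describe ticagrelor as a CYP3A and P-gp substrate, and cyclosporine as a CYP3A4 substrate and potent P-gp inhibitor. Slower elimination is therefore one plausible form of the interaction under study, though the protocol does not say that it is expected.

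If it occurs, the rule removes combination-arm AUCs because they are large, and the ticagrelor-alone value of the same subject usually stays. Missingness then depends on the value that is lost. A random subject effect does not correct that.

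The AUC ratio is a primary result and half of each no-effect rule. An attenuated ratio matters even where no-effect is correctly rejected, because the primary objectives are to investigate the size of each drug's effect on the other.

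**Working it through.** **Plan's own figure.** With CV 19%, the log-scale SD is √ln(1 + 0.19²) = 0.188. For 18 subjects the SE is 0.188 × √(2/18) = 0.0628. Exact power of the two one-sided tests at a true ratio of 1.0 is about 92% (15 or 16 df), so the 90% in Section 12.3 is reproduced. It assumes that all 18 AUC pairs are available.

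**Where the 20% limit lies** (mono-exponential decline, measurable to 48 h).
- Accumulation: 1.8 = 1/(1 − e^(−12k)), so k = −ln(1 − 1/1.8)/12 = 0.0676 per h and half-life = ln 2/k = 10.3 h.
- Share extrapolated at 48 h: e^(−48 × 0.0676) = 3.9%.
- Half-life at which 20% is extrapolated: 48 × ln 2/ln 5 = 20.7 h, a 2.0-fold increase.
- For accumulation ratios of 1.6 to 2.0, the half-life is 8.5 to 12 h, the extrapolated share 2.0% to 6.3%, and the increase needed 2.4- to 1.7-fold.

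**Share of values lost.** Let an interaction on clearance multiply AUC and half-life by f. The fraction lost is 1 − Φ(ln(20.67/(10.26 f))/s). With an assumed between-subject CV of 30%, s = √ln(1 + 0.30²) = 0.294 if within-subject variation does not enter half-life, and √(0.294² + 0.188²) = 0.349 if all of it does.
- f = 1 (ticagrelor alone): 0.9% to 2.2%.
- f = 1.25: 5.2% to 8.5%.
- f = 1.5: ln(20.67/15.39) = 0.295, so z = 1.00 to 0.85, and 16% to 20% are lost.
- f = 2.0: 49%.

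**Effect on the ratio.** Simulated trials of 18 subjects, within-subject CV 19%, each AUC above 20% extrapolation deleted. Ranges cover between-subject CV 30% to 35%, how much within-subject variation enters half-life, and the estimator: complete pairs, generalised least squares, or the protocol's mixed model by REML.

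| True ratio | Combination AUCs lost | Ticagrelor-alone AUCs lost | Estimated ratio | AUC interval within 0.80–1.25 |
|---|---|---|---|---|
| 1.25 | 5–11% | 1–4% | 1.22–1.25 | 5–9% (5% with all data) |
| 1.5 | 16–21% | 1–3% | 1.42–1.50 | 0–0.3% |
| 2.0 | 49–50% | 1–3% | 1.76–2.00 | 0 |

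With no interaction, the losses are equal and the ratio is unbiased. The upper ends of the estimates come from complete pairs when half-life carries no within-subject variation. Deletion then depends only on the subject, so the pairs that remain are unbiased. The mixed model also uses unpaired values and stays slightly low. Retaining every AUC returned the true ratio in each scenario.

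**Variations.**
- Bioavailability only, half-life unchanged: equal losses (2% per arm at 10.3 h, 24% per arm at 16 h) and no bias.
- Interaction varying between subjects with an assumed CV of 30%: as low as about 1.3 at true 1.5 and about 1.5 at true 2.0, and up to 15% of trials meeting the AUC criterion at true 1.25.
- Baseline half-life 13 h, true 1.25: 25% against 9% lost, estimate 1.20, criterion met in 11%. Baseline 8 h: 2% against 0.3%, 1.245, 5.6%.
- AUC(0-t) modelled instead, baseline 10.3 h: 1.20, 1.37 and 1.66 at true 1.25, 1.5 and 2.0. Under the same REML model, deletion gave 1.22–1.24, 1.44–1.47 and 1.81–1.89.

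**The case against.** A reader might infer that the rule certainly strips the combination arm and biases the ratio. The documents do not support that. They nowhere state that cyclosporine prolongs ticagrelor half-life, and Section 3.2 justifies the 600 mg dose by the potential effect on P-gp. An effect confined to bioavailability would leave losses balanced. This stands, and the point is therefore conditional.

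The largest figures need an added interaction CV of 30%. The apparent intra-subject variance is then 0.188² + 0.294²/2 = 0.0786, a CV of √(e^0.0786 − 1) = 28.6%, against the 19% or less planned in Section 12.3. They are an outer case. Near 1.25 the planned CV gives a shift of about 2% at most, Cmax must also pass and is untouched by the rule, and at a two-fold interaction the no-effect conclusion is not at risk. This also stands.

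The loss would not be hidden. Section 12.2.1 flags excluded data in the listings, and Section 12.2.4 summarises ticagrelor and metabolite parameters by treatment with n. But seeing an uneven n does not correct the estimate or show how far it moved.

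Finally, the 20% limit is a reliability rule, and sensitivity analyses are often left to the SAP, which is not shown. That argues against making retention the main analysis. It does not remove the point, because the protocol itself fixes the deletion, the absence of missing-data handling and the modelled parameters.

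**Conclusion.** The point holds in conditional form. The 20% rule, with no handling of the resulting gaps, can attenuate the primary ticagrelor AUC ratio if the interaction prolongs half-life, and does nothing to it if half-life is unchanged. At the planned 19% CV with a uniform interaction on clearance, the attenuation runs from nothing to about 2% at a true ratio of 1.25 (1.22/1.25), 5% at 1.5 (1.42/1.50) and 12% at 2.0 (1.76/2.00). The risk of wrongly meeting the AUC criterion at 1.25 rises from 5% to at most about 9%, and the joint risk with Cmax cannot be higher than the AUC risk.

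These figures rest on mono-exponential decline, a 10.3 h effective half-life derived from the accumulation ratio, an assumed between-subject CV of 30% to 35%, and "If %AUCext is greater than 20% then AUC will not be reported" being read as removing the value from the model. The effect of ticagrelor on cyclosporine cannot be quantified, because no cyclosporine half-life is given. This is a cheap improvement to the plan and does not invalidate the design.

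**What to change.** Keep the 20% rule for the main analysis if wished, and add:
- Section 11.2: AUC values with more than 20% extrapolated will still be calculated, flagged, and counted by analyte and treatment.
- Section 12.2.4: the same mixed model will be refitted with the flagged AUCs retained, as a pre-specified sensitivity analysis, and both results will be reported.
- Section 12.2.4: AUC(0-t), already derived, will be modelled as a companion. It should not replace AUC, since it attenuates a half-life-driven interaction more than the deletion does.
- Section 12.2.4: a no-effect conclusion will be stated only if the analysis retaining flagged AUCs agrees.

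The cost is a few sentences and a few extra model runs. The downside is that flagged AUCs carry more extrapolation error, which the simulations above do not model. Showing the results with and without them lets the reader judge it.
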